Treatment groups will be dummy coded with CC (coping control) used as the reference group. We will test for treatment condition effects on the stress and symptom outcome measures using MLMs as we did in our publications in the R21 feasibility trial. MLMs provide an optimal analytic strategy because they model all available data (following intent-to-treat principles in RCTs) and allow us to flexibly evaluate the nested nature of this data structure. Specifically, we will create (for EMA) 3-level MLMs (levels: individual participants; day; within-day time) using restricted maximum likelihood estimation. The 3-level EMA MLMs testing each aim will compare the 3 treatment intervention groups on each dependent variable (e.g., daily stress) from the pre, post, and follow-up training measurement occasion. The 3-level models will include a random intercept for day nested within participant. Measurement occasion (pre, post intervention, follow-up), group condition, day-specific factors (e.g., day-of-week or weekday versus weekend), and within-day time will be modeled as fixed effects. All models will be fit with compound symmetric variance-covariance data structure but other structures (e.g., autoregressive covariance structure, ARH(1), spectral power) will be evaluated using Akaike's Information Criterion (AIC). We have specified this initial approach for modeling random and fixed effects, but we will evaluate whether this approach best fits the data using likelihood ratio tests and AIC. In testing each aim, each measurement occasion  $\times$  treatment interaction will be evaluated with a decision rule that a significant effect is observed when the measurement occasion  $\times$  treatment interaction statistic and corresponding p-value is less than .05 (two-tailed). When a significant interaction is observed, follow-up planned contrasts in each MLM will compare specific groups at post-training. To help with benchmarking we will provide effect size statistics corresponding to the magnitude of change over time, and between groups at each post-treatment time point. One strength of our approach here is that it extends an established MLM data analytic pipeline we used in our three-arm EMA R21 trial publications with success, along with MLM mediation analyses in other MBSR RCT publications.

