**Testing our Hypotheses.** We are specifying a priori predictions about the effects of MA-MBSR intervention, relative to MO-MBSR and CC. Thus no statistical corrections for multiple comparisons will be made for our primary study hypotheses or specified pair-wise comparisons. When additional exploratory analyses are conducted, a Holm's correction will be made for multiple comparisons. We have previously published our MLM approach evaluating MA-MBSR effects relative to these two control groups (see Chin et al., 2019 or Lindsay et al., 2018 publications)—so here we highlight our equations and approach. In previous work we have focused on stress, so below we apply this approach to evaluating hypothesis #2, specifying that MA-MBSR will reduce symptoms relative to MO-MBSR and CC. This hypothesis will be tested separately for clinician assessed, physician assessed or patient self-reported symptoms (using the IBS-SS). The general form of the model to be tested, exclusive of covariates, is as follows, in mixed model

notation:

IBS symptomsit =  $\gamma_{00} + \gamma_{01} \cdot (\text{txgroup}_i) + \gamma_{10} \cdot (\text{time}_{it}) + \gamma_{11} \cdot (\text{txgroup}_i) \cdot (\text{time}_{it}) + u_{0i} + e_{it}$  where IBS symptomsit is the composite symptoms score for individual  $i$  at time-point  $t$ , timeit is the measurement occasion (pre, post intervention, or follow-up) assessment time of year, txgroupi is the treatment group a participant is assigned to. In multilevel notation:

$$\begin{aligned} \text{Level 1: } & \text{Symptoms}_{it} = \beta_{0i} + \beta_{1i} \cdot (\text{time}_{it}) + e_{it} \\ \text{Level 2: } & \beta_{0i} = \gamma_{00} + \gamma_{01} \cdot (\text{txgroup}_i) + u_{0i} \\ & \beta_{1i} = \gamma_{10} + \gamma_{11} \cdot (\text{txgroup}_i) \end{aligned}$$

The primary test of hypothesis is the F-test of the null hypothesis  $H_0: \gamma_{11} = 0$ . Note that this general model will be used, with different outcomes (e.g., stress) and for subsequent aims below but will not be repeated.

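### The stated primary test for hypothesis 2 is a non-directional group-by-occasion F-test, and the SAP does not say how the two contrasts against MO-MBSR and CC decide the hypothesis

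*SAP*

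**What the plan says.** The SAP, Testing our Hypotheses, states hypothesis 2 with one direction and two comparators: "specifying that MA-MBSR will reduce symptoms relative to MO-MBSR and CC". After writing out the model it says: "The primary test of hypothesis is the F-test of the null hypothesis" that the group-by-time coefficient is zero. It adds that the same general model serves other outcomes and later aims.

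The decision rule stands in the earlier text on mixed models, under Overview of Data Analyses. For each aim it sets "a decision rule that a significant effect is observed when the measurement occasion" by treatment interaction has p below .05, two-tailed. If that interaction is significant, "follow-up planned contrasts in each MLM will compare specific groups at post-training". Testing our Hypotheses also mentions pairwise comparisons, to say that they go uncorrected: "Thus no statistical corrections for multiple comparisons will be made for our primary study hypotheses or specified pair-wise comparisons".

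**The concern.** The hypothesis makes two directional claims about one arm. The stated test asks only whether the three arms change differently over the occasions. A significant result is compatible with the hypothesis, with its reverse, and with patterns in which MA-MBSR adds nothing to MO-MBSR.

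The contrasts could settle this, but the SAP does not tie the verdict to them. Suppose F is significant, MA-MBSR is better than CC, and MA-MBSR is not shown to be better than MO-MBSR. The stated primary rule is met, yet half of the hypothesis has not been shown. The SAP does not say whether hypothesis 2 then counts as supported, so the answer would be settled after the data are seen. Because the model and rule are reused, the same gap affects any other aim with this form.

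**Working it through.** The SAP gives no sample size, effect size or correlation, so it has no figure of its own to reproduce. Its only number here is the two-tailed .05. The first step needs no further input; the rest is illustration.

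**1. What the F-test can show.** Three arms and three categorical occasions give an interaction with 4 degrees of freedom (2 if time is linear). F is built from squared deviations, so reversing the sign of every effect leaves its rejection rate unchanged. It cannot say which arm is best.

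**2. How often it is significant.** Assumed: n = 80 per arm, equal allocation, complete data, compound symmetry, within-person correlation ρ = 0.5, and one arm differing from the other two by d = 0.4 SD at post and follow-up.
- Non-centrality = (4/9) n d² / (1 − ρ) = (4/9) × 80 × 0.16 / 0.5 = 11.38, with 4 and 2(3 × 80 − 3) = 474 df. Power is 77%.
- At 50 per arm: (4/9) × 50 × 0.16 / 0.5 = 7.11, with 294 df. Power is 54%.
- The figure is the same whether MA-MBSR is best, MA-MBSR is worst, MA-MBSR equals MO-MBSR with both better than CC, or only MO-MBSR works.
- Range for ρ = 0.3 to 0.7: 61% to 95% at 80 per arm, 40% to 79% at 50.
- The equality needs equal allocation and a single odd-one-out arm. For a graded pattern (MA-MBSR 0.4 SD, MO-MBSR 0.2, CC 0) the non-centrality is (1/3) × 80 × 0.16 / 0.5 = 8.53 and power is 63%.

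**3. If both contrasts decide.** For pre-to-post change, the standard error of a difference between two arms is √(4(1 − ρ)/n) = √(4 × 0.5/80) = 0.158. The expected statistic is 0.4/0.158 = 2.53, which gives about 71% power for one contrast. The two contrasts share the MA-MBSR arm, so the joint figures come from simulation (200,000 draws per scenario). With MA-MBSR truly better than both by 0.4 SD:

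| Per arm | ρ | F alone | Both contrasts | F, then both |
|---|---|---|---|---|
| 80 | 0.3 | 61% | 40% | 37% |
| 80 | 0.5 | 77% | 57% | 54% |
| 80 | 0.7 | 95% | 84% | 83% |
| 50 | 0.5 | 54% | 35% | 31% |

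The last column can never exceed the one before it, because it adds a condition.

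**4. False claims under that rule.** If MA-MBSR equals MO-MBSR, the contrast between them favours MA-MBSR at two-tailed .05 in 2.5% of trials, so both contrasts cannot succeed more often than that. Simulation gives 2.4% at 80 per arm and 2.3% at 50.

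**5. How often the unresolved case arises.** If MA-MBSR equals MO-MBSR and both beat CC by 0.4 SD (ρ = 0.5), 62% of trials at 80 per arm and 38% at 50 show a significant F, MA-MBSR better than CC, and MA-MBSR not shown better than MO-MBSR.

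**6. Which contrast.** The SAP compares groups at post-training, whereas the interaction concerns change. The variance of a post-training difference is 2/n, against 4(1 − ρ)/n for change; these are equal only at ρ = 0.5. At 80 per arm, power for both contrasts is 40% with change and 57% with the post-training difference at ρ = 0.3, and 84% and 57% at ρ = 0.7.

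**The case against.** The strongest reply is that a reasonable reader can already assemble the right analysis. Hypothesis 2 names both comparators and the direction, contrasts are planned, and their occasion is given. This stands: it would be wrong to say that the SAP lacks the pairs or the direction. What it lacks is the link from contrasts to verdict and a both-or-either rule.

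One may also say that two separately reported predictions would be as defensible as requiring both. That is a possible choice, but the SAP does not make it, and the hypothesis as worded covers both comparators.

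Three stronger readings are tempting and are not supported.
- A reader might infer that coding CC as the reference ("Treatment groups will be dummy coded with CC (coping control) used as the reference group") removes the comparison with MO-MBSR. It does not: that comparison is a linear contrast of the same coefficients, and contrasts are planned.
- A reader might take the rejection rates in step 2, or the 62% in step 5, as false-claim rates of this plan. They are not, because the plan goes on to run contrasts that would show where MA-MBSR stands.
- A reader might combine the separate testing of several symptom measures with the absence of correction and infer an inflated error. Which measure decides is commonly settled in the protocol, which is not shown, so no finding follows.

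**Conclusion.** The concern holds in limited form. The rule that the SAP calls primary does not establish hypothesis 2, because a non-directional joint test can be met by patterns that contradict it. This follows from the text and the nature of the test, and rests on no assumed number. The comparisons that are needed can be reached from the plan, so this is a gap in the decision rule and not a missing analysis. It should be closed before the data are analysed.

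The sizes are illustrative only. They assume equal allocation, complete data, compound symmetry, 50 or 80 per arm, and 0.4 SD at both later occasions. The power figures for both contrasts also depend on using pre-to-post change, which is not clearly the contrast that the SAP intends.

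**What to change.** In Testing our Hypotheses, replace the statement of the primary test along these lines:

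- Hypothesis 2 is decided by two contrasts, MA-MBSR versus MO-MBSR and MA-MBSR versus CC. It is supported only if both have p below .05 (two-tailed) in favour of MA-MBSR.
- If only one does, that comparison is reported on its own and hypothesis 2 is not declared supported.
- The group-by-occasion F-test is reported as supportive and is not a gate to the contrasts.
- State whether each contrast is the difference at post-training, as the SAP now words it, or the difference in change from pre to post, which matches the interaction.

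No correction between the two contrasts is needed, because both must succeed; this fits the SAP's choice not to correct. The decision rule under Overview of Data Analyses should be brought into line.

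The change is wording only and needs no new data. Its cost is that power for the claim is lower than power for the F-test (57% against 77% at 80 per arm under the assumed inputs), though never lower than F followed by both contrasts (54%). If the sample size was set on the F-test, recheck it against both contrasts.

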For hypothesis #3, we will use EMA-sampled IBS symptom severity to test whether EMA-sampled stress reduction will statistically mediate symptom improvements. We will test for concurrent relations between EMA-sampled stress and IBS symptom severity (within the same moment) and also test lagged relations (stress at time  $t$  predicting IBS symptom severity at time  $t+1$ ). To conduct this mediation analysis, we will compare two MLMs that use IBS symptom severity as the outcome and group condition as a fixed effect: one MLM will include stress as an additional fixed effect, and another will not. If the fixed effect for group condition is statistically significant in the latter but not the former, stress reduction will be declared to act as a mediator for symptom improvements.

For hypothesis testing, we will first run unadjusted models without covariates, as described above. Then, as a sensitivity analysis, we will run adjusted models that incorporate baseline characteristics related to sociodemographic covariates (sex, gender, age, race), clinical covariates (IBS subtype, baseline IBS symptom severity, baseline perceived stress), and other time-related covariates such as day-of-week when appropriate (e.g., for analyses involving EMA samples where we observe repeated measures across and within days).

**Attrition and Missing Data.** We expect minimal participant attrition (<15%) during the study period across conditions. Dropouts are not expected to be a function of the missing outcome data given the observed. Our unadjusted analyses assume data are missing completely at random, while our adjusted analyses loosen this assumption to allow for data to be missing at random. We will also assess the sensitivity of our results to violations of the missing-at-random assumption (e.g., via pattern-mixture models). Additionally, we will evaluate whether adherence to the program and EMA vary across groups. To evaluate attrition, we will compare study dropouts to study completers based on observed participant characteristics.

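### The concurrent and lagged stress–symptom tests have no named random stress slope; if coupling differs between people and none is fitted, the standard error of the average slope is too small

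*SAP*

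**What the plan says.** In the hypothesis #3 paragraph under Testing our Hypotheses, the SAP commits to two analyses of the ecological momentary assessment (EMA) data: "We will test for concurrent relations between EMA-sampled stress and IBS symptom severity (within the same moment) and also test lagged relations", the lagged version taking stress at one prompt to predict symptoms at the next. The mediation comparison in the same paragraph then uses two mixed models: "one MLM will include stress as an additional fixed effect, and another will not".

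The random part of the EMA models is described earlier in the Data Analysis Strategy: "The 3-level models will include a random intercept for day nested within participant". The general equation under Testing our Hypotheses has a single person-level random term, the intercept deviation. Its level-2 equation for the slope has no residual. Of that equation the SAP says: "Note that this general model will be used, with different outcomes (e.g., stress) and for subsequent aims below but will not be repeated". No random slope is named for any variable.

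The SAP also calls its choice of random and fixed effects an initial one and adds that "we will evaluate whether this approach best fits the data using likelihood ratio tests and AIC". The specific alternatives it lists (autoregressive, ARH(1), spectral power) are covariance structures.

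**The concern.** Stress is measured at every prompt, so its slope on symptoms can differ from person to person. When it does, the uncertainty of the average slope has two parts: prompt-level noise, which shrinks with the total number of prompts, and between-person variation in the slope, which shrinks only with the number of people. A model with random intercepts and one common slope leaves out the second part. It counts each prompt as independent evidence about the average.

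The concurrent and lagged relations are stated tests belonging to hypothesis #3. Under the model as written, their p-values and intervals could be too optimistic, and a link that runs one way in some patients and the other way in others could be reported as a general one.

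**Working it through.** **Inputs from the SAP.** The two stress tests, stress as a fixed effect, intercepts as the only named random terms, and a threshold given for the occasion-by-treatment interaction ("corresponding p-value is less than .05 (two-tailed"). I assume that threshold carries over to the stress slope. The SAP states no type I error for these tests beyond this nominal level, so there is no figure to reproduce.

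**Inputs assumed.** Prompts per person *m*, and the between-person SD of the slope, τ, in residual SDs per within-person SD of stress. The SAP gives neither. The stress predictor is taken as within-person variation.

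**Formula.** With N people, residual variance σ², within-person stress variance s², and r = (τ in those units)²:

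- true variance of the average slope = σ²(1 + m·r)/(N·m·s²)
- variance reported by the common-slope model = σ²(1 + r)/(N·m·s²), because the residual absorbs the slope variation
- ratio R = (1 + m·r)/(1 + r). N cancels, so enrolling more people does not help.
- actual two-sided type I error = 2·[1 − Φ(1.96/√R)]

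**Worked case.** m = 60, τ = 0.20: r = 0.04, R = 3.40/1.04 = 3.27, √R = 1.81, 1.96/1.81 = 1.08, type I error 27.8%.

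**Grid: type I error (%) with a common slope**

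| m | τ = 0.05 | τ = 0.10 | τ = 0.15 | τ = 0.20 |
|---|---|---|---|---|
| 12 | 5.3 | 6.3 | 7.9 | 10.0 |
| 30 | 5.8 | 8.4 | 12.6 | 17.8 |
| 45 | 6.3 | 10.2 | 16.2 | 23.2 |
| 60 | 6.7 | 11.9 | 19.6 | 27.8 |
| 180 | 10.3 | 23.9 | 37.8 | 48.5 |

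If τ is instead written in raw units with residual variance 0.6 and stress variance 1, then 0.15 becomes 0.15/√0.6 = 0.19 on the scale above. With 60 prompts this gives about 28%, using the simpler ratio 1 + m·r.

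**Simulation check.** REML fits with participant and day intercepts, 100 people assumed, mean slope zero. The last two columns let an LRT at 0.05 decide whether a random stress slope is kept.

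| m | τ | Runs | Common slope | Random slope | LRT keeps slope | Error after LRT |
|---|---|---|---|---|---|---|
| 45 | 0 | 150 | 4.0% | 4.0% | 6% | 4.0% |
| 45 | 0.05 | 150 | 8.0% | 6.7% | 9% | 8.0% |
| 45 | 0.10 | 250 | 11.6% | 6.0% | 64% | 7.2% |
| 45 | 0.20 | 250 | 20.8% | 4.8% | 100% | 4.8% |
| 60 | 0.20 | 200 | 27.0% | 7.5% | 100% | 7.5% |
| 15 | 0.10 | 300 | 5.3% | 4.7% | 18% | 5.0% |

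The simulation standard error around 5% is √(0.05 × 0.95/n), which is 1.8 points at 150 runs, 1.5 at 200 and 1.3 at 300. Three things follow:

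- The common-slope results agree with the closed form.
- The random-slope results (4.0–7.5%) are within simulation error of 5%. The 7.5% in the fifth row is the random-slope result itself, since the LRT kept the slope every time.
- At τ = 0.05 the LRT seldom keeps the slope, so the result is essentially that of the common-slope model. The closed form puts that at 6.3%, and 8.0% in 150 runs is compatible with it.

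**The case against.** The strongest reply is that the SAP does not commit to intercepts only. It calls its random effects an initial choice and promises a check by LRT and AIC. If that check tries a stress slope, it finds the heterogeneity behind the large error rates almost every time. In the simulation with τ = 0.20 it kept the slope in 100% of runs, and error fell from 20.8% to 4.8% (45 prompts) and from 27.0% to 7.5% (60 prompts). This stands, and it removes most of the upper range. It is conditional, though: the SAP does not list the stress slope among the terms to try, and at τ = 0.10 the LRT missed it in 36% of runs. Leaving the term to a choice made after seeing the data also leaves open which p-value is reported.

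Second, the wording about stress as a fixed effect belongs to the mediation comparison, and the sentence on concurrent and lagged relations specifies no model of its own. Listing a predictor as a fixed effect does not rule out a random slope for it. That is fair. A reader might infer that the SAP forces one common slope on everyone. The text supports only that no other form is named, and that the general equation, which is to be reused, has none.

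Third, a reader might infer that the inflated error rate is that of the mediation conclusion. It is not. The rule is "If the fixed effect for group condition is statistically significant in the latter but not the former", where the two models are those without and with stress, and the p-value of the stress slope plays no part. Nor does the SAP plan an interval for an indirect effect that the problem could carry into.

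Fourth, all the magnitudes rest on assumed prompts per person and slope SD. That is true, so no single range can be attributed to this trial.

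**Conclusion.** The concern holds as a gap in specification. The SAP plans tests of a prompt-level predictor, names only random intercepts, and leaves a random stress slope to a check that does not mention it. If coupling differs between people and no slope is fitted, the standard error is too small whatever the sample size.

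The size is conditional on two quantities the SAP does not give. Type I error is about 5% with few prompts and little heterogeneity. It reaches 19.6–27.8% with 60 prompts and a slope SD of 0.15–0.20, and more with denser sampling. If an LRT that includes the slope is used, it is about 5–7.5% for slope SDs of 0.10–0.20, with the small common-slope excess remaining at 0.05. If slopes do not vary, there is no inflation.

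The point is confined to the concurrent and lagged stress tests. The documents do not support extending it to the mediation rule or to the occasion-by-treatment tests.

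**What to change.** Add one sentence to the hypothesis #3 paragraph: the concurrent and lagged EMA models with stress as a predictor include a participant-level random slope for stress as the pre-specified starting model, uncorrelated with the intercept if convergence requires, with Satterthwaite or Kenward-Roger degrees of freedom. If the slope variance cannot be estimated, participant-level cluster-robust standard errors are used instead.

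The cost is one variance component and somewhat wider intervals for the stress slope. If coupling turns out not to vary, the estimated slope variance should fall near zero and little is lost. Merely naming the slope as a candidate in the existing LRT/AIC step would remove most of the problem, but would leave some inflation at small to moderate heterogeneity and keep the choice of model open until the data are seen.

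### The SAP does not say whether same-moment or lagged stress decides the hypothesis 3 mediation verdict, so a model without time order can trigger it

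*SAP*

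**What the plan says.** All of this stands in the hypothesis 3 paragraph of the SAP, under Testing our Hypotheses.

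- Two kinds of relation are planned: "concurrent relations between EMA-sampled stress and IBS symptom severity (within the same moment", and the plan will "also test lagged relations (stress at time" t with symptoms at t+1).
- The mediation analysis is then described once, as two mixed models for symptom severity with group as a fixed effect: "one MLM will include stress as an additional fixed effect, and another will not".
- The decision rule follows. "If the fixed effect for group condition is statistically significant in the latter but not the former", then "stress reduction will be declared to act as a mediator for symptom improvements".

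The stress term in the second model is not identified as the same-moment or the lagged value. Neither version is given precedence, and the two are not required to agree. No reverse-direction check is planned. The adjusted sensitivity models add demographic, time-related and "clinical covariates (IBS subtype, baseline IBS symptom severity, baseline perceived stress") covariates; symptoms at the preceding prompt are not among them. For the primary hypotheses the SAP also says that "no statistical corrections for multiple comparisons will be made for our primary study hypotheses", so no multiplicity rule restricts which version may carry the verdict.

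**The concern.** A mediator has to come before the outcome it is said to explain. When stress and symptoms are reported at the same prompt, the order is unknown, and a bout of symptoms may well raise stress at that moment. Stress is then a consequence of the outcome. Conditioning on a consequence of the outcome pulls the group coefficient towards zero even if stress has no effect on symptoms.

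A treatment that eased symptoms by some other route, and lowered stress only as a result, could therefore meet the stated rule. The trial would report stress reduction as the mechanism when the arrow runs the other way. What is at stake is the mechanism conclusion of hypothesis 3; the comparisons between treatment groups are not affected.

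**Working it through.** **Inputs.** The SAP states no sample size, prompt count, power, effect size or stress–symptom correlation for hypothesis 3, so there is no planned figure to reproduce, and every size below is an assumption. The significance threshold, "corresponding p-value is less than .05 (two-tailed"), is stated for the occasion-by-treatment interaction; its use for the group effect in hypothesis 3 is assumed. The test scenario is pure reverse causation: group → symptoms → stress, with no effect of stress on symptoms.

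**Step 1: algebra.** Let Y = cT + u (symptoms) and M = λY + e (stress).

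- Effect of group on stress: a = λc.
- Slope of Y on M given T: b = λ·var(u) / [λ²·var(u) + var(e)].
- Group coefficient after adding M: c − ab = c(1 − rho²), where rho² = λ²·var(u) / [λ²·var(u) + var(e)].
- The residual standard deviation shrinks by √(1 − rho²), so the group z becomes about z·√(1 − rho²).

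With repeated prompts and a random intercept, the relevant rho is essentially the within-person correlation. Starting from z = 2.80 (80% power):

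| rho | Shrinkage rho² | z after adding stress |
|---|---|---|
| 0.2 | 4% | 2.74 |
| 0.3 | 9% | 2.67 |
| 0.4 | 16% | 2.57 |
| 0.5 | 25% | 2.43 |
| 0.6 | 36% | 2.24 |
| 0.7 | 49% | 2.00 |

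The average z stays above 1.96 throughout. A false verdict therefore arises only in trials that start near the threshold, and the rule itself has to be simulated.

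**Step 2: the rule, single-level.** With 100 per arm and 5,000 runs at 80% power, the rule declared mediation in 0.8%, 5.8%, 15.4% and 31.0% of all trials at rho 0, 0.3, 0.5 and 0.7. At 90% power the rates were 0.6%, 4.6%, 11.3% and 29.2%.

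**Step 3: the rule with EMA-type data.** This used two arms, post-treatment prompts only, 80 per arm, 15 prompts, a random intercept, effects set for about 80% power, and 300 runs per setting. Within-person variance was 0.5 for symptoms and 0.45 for stress noise, so within-person rho² = 0.5λ² / (0.5λ² + 0.45). For λ = 0.3, 0.5 and 0.8 this is 0.045/0.495 = 0.091, 0.125/0.575 = 0.217 and 0.320/0.770 = 0.416, that is, rho of about 0.30, 0.47 and 0.64. Paired entries are for symptom autocorrelation 0 / 0.4.

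| λ | Same-moment shrinkage | Same-moment false verdict, all trials | Lagged shrinkage (autocorrelation 0.4) | Lagged false verdict (0.4) |
|---|---|---|---|---|
| 0 | 0% / 0% | 0.3% / 0.3% | 0% | 0.3% |
| 0.3 | 9.3% / 9.4% | 3.7% / 4.3% | 3.2% | 1.0% |
| 0.5 | 23.2% / 21.3% | 11.3% / 9.0% | 7.5% | 1.0% |
| 0.8 | 43.1% / 40.8% | 18.3% / 17.3% | 14.8% | 2.3% |

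The shrinkage matches rho² from step 1. With no symptom autocorrelation, lagged shrinkage was about 0%. With 300 runs, a rate of 17.3% has a standard error of √(0.173 × 0.827/300) ≈ 2.2 percentage points.

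**Step 4: rates among trials with a significant total effect.** Two separate simulations used 80 per arm, 16 post-training prompts, a person share of 0.4 in symptoms and 1,500 runs per setting. At rho 0.3, 0.4, 0.5 and 0.6 one gave false verdicts in 7%, 11%, 18% and 24%, the other in 7%, 14%, 20% and 25%. As a cross-check, step 2 gives 5.8/0.80 ≈ 7% at rho 0.3 and 15.4/0.80 ≈ 19% at rho 0.5.

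**Step 5: sensitivity.** Over the same rho range, the conditional rate was 1–5% when stress had no stable person-level variance of its own, and 10–37% when that variance was doubled. The shrinkage barely moved (8–10% at rho 0.3, 35–38% at rho 0.6).

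**The case against.** The strongest reply is that the SAP does attend to time order. It plans a lagged analysis, and the concurrent relations may be meant only as tests of association, which is the status the fix would give them. It also words the hypothesis as statistical mediation, which claims less than causation. This stands in part. A reader might infer that the SAP applies the two-model comparison to both versions of stress; the text does not say so. What it supports is ambiguity: one rule, an unidentified stress term, and nothing to stop the same-moment value from being used. The wording of the declaration is also stronger than that of the hypothesis.

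A reader might also infer that part of the benefit will be credited to stress. The rule gives a yes/no verdict and reports no mediated share. The rho² figures describe how the coefficient shrinks; the consequence to weigh is the false-verdict rate.

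Third, that rate is a minority outcome even in an extreme scenario in which stress does nothing, and the simulations are simpler than the three-arm, three-occasion, three-level EMA analysis in the SAP. This is right: the percentages do not estimate this trial's error rate. The direction of the bias under this scenario follows from the algebra for any nonzero rho.

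Finally, the lagged model is not clean either. This also stands: with autocorrelated symptoms and no prior symptoms in the model, lagged stress still absorbed 3–15% of the group effect, although false verdicts fell to 1.0–2.3%.

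**Conclusion.** The point holds as a gap in the decision rule. The SAP leaves open which stress value enters the comparison and which version decides, so a same-moment model can lead to the mediator declaration although it cannot separate stress driving symptoms from symptoms driving stress. If symptoms drive stress and stress does nothing, the rule gives a wrong verdict in roughly 4–18% of all simulated EMA trials (λ 0.3 to 0.8), or about 7–25% of those with a significant total effect (rho 0.3 to 0.6). These rates rest on assumed sample sizes, correlations and variances, and above all on how much stable person-level variance stress has of its own.

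It would go too far to say that the plan ignores time order or that its mechanism conclusion will probably be reversed. Nor would estimating an indirect effect in place of the loss-of-significance rule settle the matter: with same-moment stress that estimate carries the same rho² bias. The point is worth correcting before analysis, but it does not threaten the main treatment comparisons.

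**What to change.** Add two sentences to the hypothesis 3 paragraph, to this effect:

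- Only the comparison with stress at one prompt and symptoms at the next can support a declaration of mediation, with the models with and without stress fitted to the same set of prompts. Otherwise the group effect could lose significance merely because prompts without a preceding stress report drop out.
- The concurrent model is reported as an association and cannot support the declaration.

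The SAP should also acknowledge that the lagged comparison reduces the bias but does not remove it when symptoms are autocorrelated and prior symptoms are not modelled.

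A reverse-direction model, with symptoms as the candidate mediator of the group effect on stress, may be reported descriptively. It has a different outcome, so its fit should not be compared with that of the planned model, and it cannot rule out a shared cause of stress and symptoms at the same prompt.

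The cost is a short text change and at most one extra model on data already collected. The downside is fewer usable prompts, which makes a mediation claim somewhat harder to reach.
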